10.2 Secondary criteria

The secondary endpoints are changes from baseline to week 48 in:

- ONLS score,
- MRC subscore (total muscle) and total score,
- INCAT Sensory Sum (ISS) Score,
- Posturography parameters:
 - o Analysis of Walking: all parameters in the condition spontaneous speed
 - o Analysis of Balance: center of pressure on anterior/posterior axis and center of pressure covered area in the four conditions (Open/Closed eyes and Spread Feet (60s)/Feet together (60s))
- Timed 10-meter walk test (s) (whatever the assistance),
- Distance 6-min walk test (m) (whatever the assistance),
- Supernormality (%),
- Strength-duration time constant (ms),
- Rheobase (mA),
- Refractoriness (%),
- Minimal absolute refractory period (ms),
- Maximal absolute refractory period (ms).

ONLS score, MRC score, INCAT Sensory Sum score, timed 10-meter walk test and distance 6-min walk test will be described at baseline and each post-baseline visit by disease group and overall on the FAS population. The absolute changes from baseline will be provided at week 48.

Posturography parameters and excitability testing (Supernormality, Strength-duration time constant, Rheobase, Refractoriness, Minimum and maximum absolute refractory period) will be described at baseline, week 24 and week 48 by disease group and overall on the FAS population. The absolute changes from baseline to week 48 will be also produced. Regarding the posturography parameters of the analysis of balance, the absolute changes from baseline to week 48 will be also produced only if ‘orthostatic position, bare foot on a force platform’ is reported and not when the test was conducted in a different condition specified under “other”. A Wilcoxon signed rank test will be performed overall for each secondary criterion to assess if the absolute change from baseline is statistically significant at week 48.

In addition, a boxplot will be provided for each parameter displaying Q1, median and Q3 values at each visit by disease group.

Absolute change from baseline will be calculated as (value at week 48 – value at baseline).

Listings of secondary criteria will be provided.

11 COMPLIANCE

All patients should receive active drug 300mg/day, one capsule in the morning, one capsule at noon and one capsule in the evening (capsule of 100mg).

Three bottles, each containing 90 capsules, are dispensed to the patient at each post-baseline visit for three months. The patient is asked to use only one bottle per month. All unused investigational products are returned and checked by the investigator. The number of returned capsules and interruption periods (if applicable) are reported on the CRF at each visit.

The cumulative number of interrupted days per patient will be calculated as the sum of number of days of each interruption, with the number of days of an interruption = date restarted – date of last dose intake - 1

The actual treatment duration (weeks) will be calculated as the [extent of exposure in weeks – (cumulative number of interrupted days/7)], with extent of exposure calculated as defined in section 12.1.

The global compliance (%) will be calculated as (Actual number of capsules taken / Theoretical number of capsules taken during the actual extent of exposure) x 100

With:

- Actual number of capsules taken = Sum of number of capsules dispensed at each visit (V2 to V5) – Sum of number of returned capsules at each post-baseline visit (V3 to V6).
- Theoretical number of capsules taken will be calculated as follows:
 - o If the time of the first study drug intake is morning:
 - if the time of the last study drug intake is evening, then theoretical number of capsules taken = [(date of last study drug intake – date of first study drug intake + 1) * 3]
 - if the time of the last study drug intake is noon, then theoretical number of capsules taken = [(date of last study drug intake – date of first study drug intake) * 3] + 2
 - the time of the last study drug intake is morning, then theoretical number of capsules taken = [(date of last study drug intake – date of first study drug intake) * 3] + 1
 - o If the time of the first study drug intake is noon:
 - if the time of the last study drug intake is evening, then theoretical number of capsules taken = [(date of last study drug intake – date of first study drug intake) * 3] + 2
 - if the time of the last study drug intake is noon, then theoretical number of capsules taken = [(date of last study drug intake – date of first study drug intake) * 3] + 1
 - if the time of the last study drug intake is morning, then theoretical number of capsules taken = [(date of last study drug intake – date of first study drug intake) * 3]
 - o If the time of the first study drug intake is evening:
 - if the time of the last study drug intake is evening, then theoretical number of capsules taken = [(date of last study drug intake – date of first study drug intake) * 3] + 1

- if the time of the last study drug intake is noon, then theoretical number of capsules taken = [(date of last study drug intake – date of first study drug intake) * 3]
- if the time of the last study drug intake is morning, then theoretical number of capsules taken = [(date of last study drug intake – date of first study drug intake) * 3] - 1

Descriptive summaries will be produced on the Safety Set population by disease group and overall for the following parameters: cumulative number of interrupted days per patient, actual treatment duration (weeks) and global compliance (%). A listing will be also provided.

12 SAFETY ANALYSIS

All safety analyses will be performed on Safety Set population.

12.1 Extent of exposure

The extent of exposure (weeks) will be calculated as (date of last study drug intake – date of first study drug intake + 1) / 7

The cumulative dose per patient (g) will be calculated as (actual number of capsules taken x 100mg) / 1000, with actual number of capsules taken calculated as defined in section 11.

Descriptive statistics will be tabulated by disease group and overall on Safety Set population and a listing will be given.

12.2 Adverse events

Any adverse event (AE) having been reported during the study for a given patient, will be classified by Preferred Term (PT) and corresponding System Organ Class (SOC) using the MedDRA terminology version 22.0.

Any AE recorded in the Adverse Events section of the CRF will be regarded as Treatment Emergent (TEAE) if it occurs during study drug period, or worsens after the first study drug intake.

The study drug period is defined as period from the day of the first study drug intake until 30 days (included) after the last study drug intake.

AEs occurring before the first study drug intake and worsening after the first study drug intake are reported as new AEs in the CRF with start date = worsening date.

Other AEs occurring during study and before the first study drug intake will be defined as pre-TEAEs (different from medical history).

AEs occurring beyond 30 days after the last study drug intake will be assigned as post-TEAEs.

In case of missing start/end date of AEs, imputation will be considered (see section 3.2) to define the emergence of AEs.

An AE will be defined as study drug related if the causality recorded in the CRF is "Definite", "Probable", "Likely", "Possible", "Conditional" or missing. The AE will be defined as "Not Related" if the causality is "Unlikely" or "Not related".

An AE will be defined as leading to a study drug discontinuation if "Drug withdrawn" is reported in the CRF.

AE duration will be computed in days as (end date – start date + 1).

A summary table describing an overview of the incidence of AEs in terms of the number and percentage of patients with at least one AE and number of events will be provided by disease group and overall with:

- Pre-TEAEs
- TEAEs
- TEAEs according to the intensity (Mild, Moderate, Severe)
- Serious TEAEs
- Study drug related TEAEs
- TEAEs leading to study drug discontinuation
- TEAEs leading to death
- Study drug related serious TEAEs
- Serious TEAEs leading to study drug discontinuation
- Study drug related serious TEAEs leading to study drug discontinuation
- Post-TEAEs

The number and percentage of patients with at least one AE and the number of events will be summarized according to SOC and PT for:

- All Pre-TEAEs
- TEAEs
- Serious TEAEs
- Study drug related TEAEs
- TEAEs leading to a study drug discontinuation
- TEAEs leading to death
- Post-TEAEs

A listing of all AEs will be performed, as well as SAEs.

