6.2 Handling of Non-Serious Adverse Events

All AEs encountered during the clinical study will be reported on the CRF.

- All AEs and SAEs must be recorded on patient’s source documents.
- All AEs and SAEs for patients who receive a treatment assignment code will be recorded in the CRFs. During the active reporting period specified above, all AEs will be reported on the AE page(s) of the CRF. It should be noted that the form for collection of SAE information is not the same as the AE CRF. Where the same data are collected, the forms must be completed in a

consistent manner. For example, the same AE term should be used on both forms. AEs should be reported using concise medical terminology on the CRFs as well as on the form for collection of SAE information.

- Each AE is to be assessed to determine if it meets the criteria for SAEs. If an SAE occurs, expedited reporting will follow local and international regulations, as appropriate.
- Withdrawal due to AE should be distinguished from withdrawal due to insufficient response, according to the definition of AE noted earlier, and recorded on the appropriate AE CRF page.

The information to be entered in the CRF will include:

- The time of onset of any AE or the worsening of a previously observed AE
- The specific type of reaction in standard medical terminology
- The duration of the AE (start and stop dates)

6.2.1 *Severity assessment*

The severity of the adverse event (AE). The severity should be rated as:

- **Mild:** discomfort noted, but no disruption of normal daily activity.
- **Moderate:** discomfort noted of sufficient severity to reduce or adversely affect normal activity.
- **Severe:** incapacitating, with inability to work or perform normal daily activity.

6.2.2 *Causality assessment*

An assessment of the relationship of the adverse event (AE) to the study medication, i.e., according to the definitions below:

Definite: a clinical event, including laboratory test abnormality, occurring in a plausible time relationship to drug administration, and which cannot be explained by concurrent disease or other drugs or chemicals. The event must be pharmacologically or phenomenologically plausible, and its clinical response to withdrawal of the drug (dechallenge) should be clinically plausible. It must also be confirmed by a satisfactory rechallenge procedure.

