Probable/likely: a clinical event in which a relationship to the IMP seems probable because of such factors as a clear temporal association with the use of the IMP, lack of alternative explanations for the event or other factors.

Possible: the essential distinctions between ‘Probable’ and ‘Possible’ are that in the latter case there may be another equally likely explanation for the event (could also be explained by disease or other drugs) and/or there is no information or uncertainty with regard to what has happened after stopping.

Unlikely: a clinical event with a temporal relationship to IMP administration that makes a causal relationship improbable and / or in which other factors suggesting an alternative aetiology exist. Such factors include a known relationship of the adverse event to concomitant drug, the patient’s disease state or environmental factors including common infectious diseases.

Conditional/Unclassified: A clinical event, including laboratory test abnormality, reported as an adverse reaction, about which more data are essential for a proper assessment or the additional data are under examination.

Unassessable: A report suggesting an adverse reaction which cannot be judged because information is insufficient or contradictory, and which cannot be supplemented or verified.

Not related: Not suspected to be reasonably related to the IMP. A reasonable alternative explanation must be available.

In addition, if the investigator determines an SAE is associated with study procedures, the investigator must record this causal relationship in the source documents and CRF, as appropriate, and report such an assessment in accordance with the SAE reporting requirements, if applicable.

As far as possible, all investigators should follow-up participants with AEs until the event is resolved or until, in the opinion of the investigator, the event is stabilized or determined to be chronic. Details of AE resolution must be documented in the CRF. Participants should be followed-up for 30 days after receiving the last dose of study medication and any AEs, which occur during this time, should be reported according to the procedures outlined above. Any significant changes in AEs should be reported even though the patient has completed the study, including the protocol-required post-treatment follow-up.

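### SAP 12.2 assigns the protocol causality category 'Unassessable' to neither the related nor the not-related class, although missing causality counts as related

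*SAP*

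**What the plan says.** Protocol 6.2.2 (Causality assessment) gives the investigator seven categories: Definite, Probable/likely, Possible, Unlikely, Conditional/Unclassified, Unassessable and Not related. Two of them are for events on which no firm judgement can be made:

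- "Conditional/Unclassified: A clinical event, including laboratory test abnormality, reported as an adverse reaction", for which more data are needed or are being examined.
- "Unassessable: A report suggesting an adverse reaction which cannot be judged because information is insufficient or contradictory", where the information cannot be supplemented or verified.

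SAP 12.2 (Adverse events) reduces the recorded causality to two classes. The related class is introduced by "An AE will be defined as study drug related if the causality recorded in the CRF is" and consists of "Definite', 'Probable', 'Likely', 'Possible', 'Conditional' or missing". The not-related class applies "if the causality is 'Unlikely' or 'Not related". No catch-all covers any other value.

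The related class feeds three rows of the adverse event overview: drug-related TEAEs, drug-related serious TEAEs, and drug-related serious TEAEs leading to discontinuation. It also feeds the table of drug-related TEAEs by SOC and PT (Table 14.5.2.5). SAP section 2, which records changes to conduct and analysis, mentions no change to the causality scale.

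**The concern.** The SAP takes a cautious line where causality is uncertain: a blank field counts as related, and so does 'Conditional'. 'Unassessable' expresses the same kind of uncertainty, and by the protocol's definition it also carries a suggestion of a reaction. Yet it is in neither list. Read literally, the rule makes an event related when the investigator leaves the field empty, but not when the investigator records a suspected reaction that cannot be judged.

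The drug-related counts are at stake. Safety is the secondary objective, the safety analysis is purely descriptive, and SAP 2.1 says that the planned DSMB was not set up. The tables are therefore the main summary of possible drug effects, and with 15 patients a single reclassified patient is visible in the percentages.

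**Working it through.** The plan gives no figure to reproduce. The check compares the protocol scale with the two SAP lists, followed by simple arithmetic on the group sizes.

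**Step 1: map each value.**

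| Protocol 6.2.2 category | SAP 12.2 term | SAP class |
|---|---|---|
| Definite | Definite | related |
| Probable/likely | Probable; Likely | related |
| Possible | Possible | related |
| Conditional/Unclassified | Conditional | related |
| Unlikely | Unlikely | not related |
| Not related | Not related | not related |
| Unassessable | none | none |
| (field blank) | missing | related |

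Six of the seven categories, plus missing, are classified. One is not: 7 − 6 = 1, namely 'Unassessable'.

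**Step 2: follow an 'Unassessable' TEAE through the outputs.** It does not satisfy the related definition, so it is absent from the three drug-related overview rows and from Table 14.5.2.5. It does not satisfy the not-related definition either. Its causality plays no part in the other outputs. It is therefore still counted among all TEAEs and TEAEs by intensity and, where applicable, among serious TEAEs, TEAEs leading to discontinuation and TEAEs leading to death. It also appears in the adverse event listing (Listing 16.2.7) and, if serious, in the SAE listing (Listing 14.5.2.9).

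**Step 3: size per patient.** Inputs: 15 patients, 5 per disease group (SAP 1.3). Assumption: all 15 received at least one dose, so the Safety Set denominators are 15 and 5. For a patient whose only potentially related TEAE is 'Unassessable', the incidence of drug-related TEAEs falls by:

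- overall: 1/15 = 0.067, or 6.7 percentage points
- within the disease group: 1/5 = 0.20, or 20 percentage points

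If the patient has another TEAE already classed as related, the patient-level incidence does not change. The count of related events still falls by one for each such event.

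**Step 4: frequency.** The documents do not say how many events were recorded as 'Unassessable', or whether the CRF allows the entry. The total effect is the Step 3 figure multiplied by an unknown number of patients, which may be zero.

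**The case against.** The strongest objection is that the rule refers to the causality recorded in the CRF, not to the protocol scale. The SAP was written in agreement with CRF version 1.0, which is not among the documents. The SAP wording differs a little from the protocol: it lists 'Probable' and 'Likely' separately, and 'Conditional' alone. That may mean it follows the CRF's own options. If the CRF has no 'Unassessable' option, the gap has no numerical effect. This stands as a condition on the consequence. It does not remove the textual gap, because the protocol defines the category and the SAP nowhere says that it was dropped.

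A second objection is that an analyst could treat an event that cannot be judged as missing, which would make it related, and that SAP 3.2 allows other missing or inconsistent data to be discussed before database lock. That is a reasonable way to resolve the matter, but SAP 12.2 does not state it. A rule fixed in advance should not depend on that guess.

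Three stronger readings are tempting, and the documents do not support them:

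- A reader might infer that 'Unclassified' events are lost as well. The protocol has one joint category, Conditional/Unclassified, and the SAP maps it to related through 'Conditional'. Naming the second half would only tidy the wording.
- A reader might infer that the SAP counts 'Unassessable' events as not related and so is biased against detecting harm. The SAP is silent on them. They are unclassified, and no bias has been shown.
- A reader might infer that such events vanish from the safety report. They drop out of the drug-related counts only (Step 2 of the working). In an uncontrolled study with descriptive safety analysis, no test or comparison between arms rests on those counts.

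**Conclusion.** The point holds: the rule is wrong as written, and the matter is minor. One of seven protocol causality categories has no class in SAP 12.2. The omission conflicts with the SAP's own treatment of missing and 'Conditional' causality.

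The textual gap is certain. Its effect on the results is conditional: it requires that CRF version 1.0 offers 'Unassessable', that at least one TEAE was recorded that way, and that the program follows the SAP literally. For the patient-level percentages it also requires that the patient has no other related TEAE. Under those conditions, and with all 15 patients in the Safety Set, each such patient lowers the related incidence by 6.7 points overall and 20 points in a group of 5. These are per-patient amounts, not an estimate of how far the reported incidence is off.

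**What to change.** In SAP 12.2, add 'Unassessable' to the list of causalities counted as related, in line with the rule for missing causality. If CRF version 1.0 does not offer the option, say so in the same place instead; that also closes the gap. With the addition, all seven protocol categories plus missing have a class.

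If the SAP has already been validated, protocol 7.1.9 provides the route: a complementary SAP describing the change.

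The cost is one added term in the text and a matching line in the program, with no new data. The downside is a possibly slightly higher related-event count, in the cautious direction that the SAP already takes for missing causality.

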12.3 Vital signs and clinical examination

Vital signs (temperature in °C, heart rate per minute and SBP/DBP in mmHg) will be summarized at baseline and each post-baseline visit by disease group and overall.

Clinical examination results (normal / abnormal) will be also tabulated by disease group and overall.

A listing of patients with abnormal clinical examination results will be given.

12.4 Laboratory evaluation

Following laboratory parameters will be described at baseline and week 48 by disease group and overall: RBC, hemoglobin, WBC, platelets, electrolytes (Na, K and Cl), protein, creatinine, glomerular filtration rate, fasting blood glucose, AST, ALT, total bilirubin, gamma glutamyl transferase (GGT), alkaline phosphatase, triglyceride, cholesterol and INR). In addition, a scatterplot displaying values at baseline and at week 48 per patient will be provided for the following same parameters, except glomerular filtration rate.

Number of abnormal values ($< LLN$ or $> ULN$) will be summarized for each parameter by disease group and overall.

A listing of patients with abnormal laboratory results will be provided.

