5.6 Visits schedule and evaluations

5.6.1 Patient follow-up schedule

	Week -4	Week 0	Week 12	Week 24	Week 36	Week 48
	Selection	Inclusion	Follow-up			End
STUDY WINDOWS		+/-5 days	+/-10 days			+/- 15 days
Informed consent	X					
Inclusion criteria	X	X				
Non-inclusion criteria	X	X				
Medical history	X					
Clinical examination	X	X	X	X	X	X
Neurophysiological examination		X		X		X
MRC sum score		X	X	X	X	X
INCAT sensory Score		X	X	X	X	X
Posturography score		X		X		X
ONLS score		X	X	X	X	X
Timed 10-meter walk test		X	X	X	X	X
6-min walk test		X	X	X	X	X
Excitability testing		X		X		X
AEs reporting		X	X	X	X	X
Concomitant therapies	X	X	X	X	X	X
Biological test ¹	X ²					X
Serum sample	X			X		X
Study drug dispensation		X	X	X	X	
Compliance check			X	X	X	X

¹ Biological safety panel includes: RBC, hemoglobin, mean corpuscular volume, WBC, platelets, electrolytes (Na, K, HCO₃, Ca), protein, creatinine, glomerular filtration rate, fasting blood glucose, AST, ALT, total and free bilirubin, gamma glutamyl transferase, alkaline phosphatase, triglyceride, cholesterol, PT, aPTT, INR

² Biological aetiology additional panel: Serum protein electrophoresis, IgA measurement, HbA1c, HBsAg, HIV, HCV tests, fibrinogen

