The patient will be supplied with the study drugs dispensed by the hospital.

Women of childbearing potential will be provided with 3 urinary pregnancy tests to be used at home every month until next visit to eliminate any risk of pregnancy during the study.

5.6.6 *Visit 5 (W36 ± 10 days)*

The investigators will record the following information into the CRF:

- Clinical examination
- MRC sum score
- INCAT sensory Score
- ONLS score
- Timed 10-meter walk test
- 6-min walk test
- AEs reporting
- Concomitant therapies
- Study drug dispensation

The investigator will provide patient with a drug delivery form for the hospital pharmacy.

The patient will be supplied with the study drugs dispensed by the hospital pharmacy.

Women of childbearing potential will be provided with 3 urinary pregnancy tests to be used at home every month until next visit to eliminate any risk of pregnancy during the study.

5.6.7 *Last visit – Visit 6 (W48 ± 15 days)*

The investigator will record the following information into the CRF:

- Clinical examination
- Neurophysiological examination
- MRC sum score
- INCAT sensory Score
- Posturography score
- ONLS score
- Timed 10-meter walk test
- 6-min walk test
- Excitability testing
- AEs reporting
- Concomitant therapies
- Biological safety panel testing:
 - o RBC, hemoglobin, mean corpuscular volume, WBC, platelets, electrolytes (Na, K, Cl, HCO₃), protein, creatinine, glomerular filtration rate, fasting blood glucose, AST, ALT, total and free bilirubin, gamma glutamyl transferase, alkaline phosphatase, triglyceride, cholesterol, PT, aPTT, INR
 - o For women of childbearing potential: highly sensitive pregnancy test (HCG)
- Serum sample
- Compliance check

5.6.8 *Duration of the study*

Duration of the inclusion phase: 12 Weeks

Duration of baseline period: 4 Weeks

Duration of treatment: 48 Weeks

Total duration of the trial: 64 Weeks

The end of the study corresponds to the end of the treatment's duration of the last patient included.

5.7 **Efficacy evaluations**

5.7.1 *Main evaluation of efficacy: description and methods*

5.7.1.1 *Neurophysiological examination*

This examination will be performed according to specific centre protocol as described below according to initial diagnosis and patient status.

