5.8.2 Safety endpoints

Standard clinical and adverse event monitoring will be done at each visit.

Standard laboratory testing (plasma biochemistry and haematology) will be done at W0 and W48 and consists in measurement of:

- Safety panel: RBC, hemoglobin, mean corpuscular volume, WBC, platelets, electrolytes (Na, K, Cl, HCO₃), protein, creatinine, glomerular filtration rate, fasting blood glucose, AST, ALT, total and free bilirubin, gamma glutamyl transferase, alkaline phosphatase, triglyceride, cholesterol, PT, aPTT, INR

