Table 14.5.5.1.2 – Laboratory parameters: Hemoglobin (g/dL) – SS population

Table 14.5.5.1.3 – Laboratory parameters: WBC (10⁹/L) – SS population

Table 14.5.5.1.4 – Laboratory parameters: Platelets (10⁹/L) – SS population

Table 14.5.5.1.5 – Laboratory parameters: Na (mmol/L) – SS population

Table 14.5.5.1.6 – Laboratory parameters: K (mmol/L) – SS population

Table 14.5.5.1.7 – Laboratory parameters: Cl (mmol/L) – SS population

Table 14.5.5.1.8 – Laboratory parameters: Protein (g/L) – SS population

Table 14.5.5.1.9 – Laboratory parameters: Creatinine (μmol/L) – SS population

Table 14.5.5.1.10 – Laboratory parameters: Glomerular filtration rate (mL/min/1.73m²) – SS population

Table 14.5.5.1.11 – Laboratory parameters: Fasting blood glucose (mmol/L) – SS population

Table 14.5.5.1.12 – Laboratory parameters: AST (IU/L) – SS population

Table 14.5.5.1.13 – Laboratory parameters: ALT (IU/L) – SS population

Table 14.5.5.1.14 – Laboratory parameters: Total bilirubin (μmol/L) – SS population

Table 14.5.5.1.15 – Laboratory parameters: GGT (IU/L) – SS population

Table 14.5.5.1.16 – Laboratory parameters: Alkaline phosphatase (IU/L) – SS population

Table 14.5.5.1.17 – Laboratory parameters: Triglyceride (mmol/L) – SS population

Table 14.5.5.1.18 – Laboratory parameters: Cholesterol (mmol/L) – SS population

Table 14.5.5.1.19 – Laboratory parameters: INR (%) – SS population

Figure 14.5.5.2.1 – Laboratory parameters: RBC (10¹²/L) – SS population

Figure 14.5.5.2.2 – Laboratory parameters: Hemoglobin (g/dL) – SS population

Figure 14.5.5.2.3 – Laboratory parameters: WBC (10⁹/L) – SS population

Figure 14.5.5.2.4 – Laboratory parameters: Platelets (10⁹/L) – SS population

Figure 14.5.5.2.5 – Laboratory parameters: Na (mmol/L) – SS population

Figure 14.5.5.2.6 – Laboratory parameters: K (mmol/L) – SS population

Figure 14.5.5.2.7 – Laboratory parameters: Protein (g/L) – SS population

Figure 14.5.5.2.8 – Laboratory parameters: Creatinine (μmol/L) – SS population

Figure 14.5.5.2.9 – Laboratory parameters: Fasting blood glucose (mmol/L) – SS population

Figure 14.5.5.2.10 – Laboratory parameters: AST (IU/L) – SS population

Figure 14.5.5.2.11 – Laboratory parameters: ALT (IU/L) – SS population

Figure 14.5.5.2.12 – Laboratory parameters: Total bilirubin (μmol/L) – SS population

Figure 14.5.5.2.13 – Laboratory parameters: GGT (IU/L) – SS population

Figure 14.5.5.2.14 – Laboratory parameters: Alkaline phosphatase (IU/L) – SS population

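### The SAP summarises 19 of the protocol's 24 safety-panel parameters, leaves out aPTT although the safety objective names it, declares none of this, and labels INR as a percentage

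*SAP*

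**What the plan says.** **Protocol.** Section 4.2 makes laboratory testing part of the safety objective, as a means of detecting drug intolerance, and its coagulation line consists of aPTT and INR. Sections 5.6.2, 5.6.7 and 5.8.2 give the full safety panel. It begins "Safety panel: RBC, hemoglobin, mean corpuscular volume, WBC, platelets, electrolytes" (here Na, K, Cl and HCO₃), continues "protein, creatinine, glomerular filtration rate, fasting blood glucose, AST, ALT" and ends "total and free bilirubin, gamma glutamyl transferase, alkaline phosphatase, triglyceride, cholesterol, PT, aPTT, INR". The footnote to the flow chart in 5.6.1 gives a variant with calcium in place of chloride: "electrolytes (Na, K, HCO₃, Ca), protein, creatinine, glomerular filtration rate". Section 7.1.6 commits to showing and describing all safety data.

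**SAP.** Section 12.4 begins its list "RBC, hemoglobin, WBC, platelets, electrolytes (Na, K and Cl), protein, creatinine" and closes it with "alkaline phosphatase, triglyceride, cholesterol and INR". It asks for summaries at baseline and week 48, a count of values outside the reference limits for each parameter, a scatterplot for every listed parameter except GFR, and a listing of patients with abnormal results. Section 13 lists 19 laboratory tables, the last being "Table 14.5.5.1.19 – Laboratory parameters: INR (%) – SS population". Figure 14.5.5.2.17 carries the same unit. Section 8 says that baseline biological testing is covered in the safety analyses and excludes only the aetiology panel. Section 1.2 reproduces the flow-chart footnote with the full panel, PT and aPTT included. Sections 2.1 and 2.2, which set out the changes from the protocol, do not mention laboratory parameters.

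**The concern.** Safety is the trial's secondary objective, and the safety panel is scheduled only twice, at baseline and at week 48. SAP 2.1 also records that no DSMB was set up, so the planned outputs carry more of the safety review. If the SAP is followed as written, a shift in aPTT, MCV or bicarbonate that stays within the reference range would appear in no planned summary. A value outside the range would appear in no planned abnormal count.

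The omission also looks unintended or unreported rather than decided. SAP 2.1 declares something as small as the missing weight measurement, and SAP 2.2 declares a renamed analysis population, so a reader would expect dropped laboratory tests to be declared there too.

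The INR label adds a second doubt. The abbreviation lists of both documents define INR as a ratio, yet its two outputs give a percentage unit. With PT and aPTT gone, INR is the only coagulation result left in the tables.

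**Working it through.** The documents state no figure for this point, so the check compares the lists. Total and free bilirubin count as two parameters, and each electrolyte counts as one.

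| Group | Protocol 5.6.2, 5.6.7, 5.8.2 | n | SAP 12.4, n | Not carried over |
|---|---|---|---|---|
| Haematology | red cells, Hb, MCV, white cells, platelets | 5 | 4 | MCV |
| Electrolytes | Na, K, Cl, HCO₃ | 4 | 3 | HCO₃ |
| Protein, renal, glucose | protein, creatinine, GFR, glucose | 4 | 4 | none |
| Liver | AST, ALT, total and free bilirubin, GGT, ALP | 6 | 5 | free bilirubin |
| Lipids | triglyceride, cholesterol | 2 | 2 | none |
| Coagulation | PT, aPTT, INR | 3 | 1 | PT, aPTT |
| Total | | 24 | 19 | 5 |

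1. **Visit and safety-endpoint lists.** 24 − 19 = 5, and 5/24 = 20.8%. The SAP list contains nothing that this panel lacks. The output list agrees with SAP 12.4: Tables 14.5.5.1.1 to 14.5.5.1.19 cover the same 19 parameters.

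2. **Flow-chart footnote.** This list also has 24 entries, with Ca in place of Cl. The SAP lacks the same five plus Ca, which makes 6. The two protocol lists together hold 25 parameters, so covering both would take six additions.

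3. **Protocol 4.2.** This list is shorter. Counting the ionogram and bilirubin as one entry each, it has 3 (blood count) + 3 (ionogram, creatinine, glucose) + 5 (liver) + 2 (lipids) + 2 (coagulation) = 15 entries. The ionogram is not broken down, so HCO₃ and Ca cannot be placed for certain. The only unambiguous loss against this list is aPTT, 1 of 15.

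4. **Declared changes.** SAP 2.1 covers the MRC version, the DSMB, weight, the posturography equipment and measure, and the merged visits. SAP 2.2 covers the population name, the Wilcoxon test and LOCF for secondary criteria. Neither covers the laboratory panel. The one exclusion in SAP 8, the aetiology panel, does not explain the gap: that panel consists of protein electrophoresis, IgA, HbA1c, the viral tests and fibrinogen, and contains none of the five.

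5. **Scatterplots.** SAP 12.4 implies 19 − 1 (GFR) = 18 figures. The output list has 17 (Figures 14.5.5.2.1 to 14.5.5.2.17), and the one missing is chloride.

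6. **Number of values affected.** At most 15 patients × 5 parameters × 2 time points = 150. This is an upper bound that assumes every patient had all five tests at both visits, which the documents do not show.

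**The case against.** Several counter-arguments deserve weight.

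- **The tests may not have been captured.** The SAP was written against a CRF that is not among the documents, and the 19 parameters may simply be what that CRF recorded. This stands, and it decides which remedy applies. It does not excuse the silence in SAP 2.1, because a planned safety measure that was not taken is itself a change to declare.
- **Individual abnormal values have other routes.** The listing of patients with abnormal laboratory results is not expressly limited to the 19 parameters. Protocol 6.1 also counts an abnormal laboratory finding as a possible adverse event. This stands too. A reader might infer that the report could declare the laboratory data clean for tests that nobody looked at, and the documents do not go that far. Neither route would give group summaries or show shifts within the normal range.
- **Some of the losses are small.** On general laboratory knowledge, which the documents do not state, PT overlaps with INR, and free bilirubin is part of the total bilirubin that is kept. That leaves aPTT, HCO₃ and MCV as the substantive gaps.
- **The denominator depends on the list.** As shown above, protocol 4.2 is shorter than 24, so 21% describes the visit-list panel and not every protocol list.
- **INR (%).** A reader might infer that the variable is really prothrombin activity in percent, so that high and low change places. The documents support only a unit that does not fit a ratio, in two output titles. SAP 12.4 names INR without a unit, the table shells are in a separate document, and nothing says that prothrombin activity was recorded. This is a query about a label, and no reversal is established.

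**Conclusion.** The point holds as a departure from the protocol in safety reporting. Five of the 24 parameters in the visit-list panel (21%) have no planned table, figure or abnormal count, or six if calcium was collected. aPTT is the most important because protocol 4.2 names it. The omission conflicts with the commitment in protocol 7.1.6 and with SAP 8, and it is undeclared in SAP 2.1 and 2.2. The counts rest only on the lists as printed.

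How much information is lost depends on what the CRF captured, which the documents do not show: anything from none to the 150-value ceiling for the five parameters. Safety analysis in this 15-patient uncontrolled study is descriptive, so no test, error rate or efficacy conclusion is affected. The INR unit and the missing chloride figure are smaller items to verify and correct alongside. It is worth correcting before the report is written, because the remedy is cheap whichever way the CRF question falls.

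**What to change.** 1. Check the CRF and database for MCV, HCO₃, free bilirubin, PT, aPTT and Ca.
2. Add each one that was collected to the SAP 12.4 list, with its summary table, abnormal count and scatterplot in section 13, and state that Listing 14.5.5.3 covers all collected parameters.
3. Declare in SAP 2.1 each one that was not collected, as was done for weight. State there whether Ca or Cl was the intended electrolyte, since the flow-chart footnote and the visit text differ.
4. Trace the source field behind Table 14.5.5.1.19 and Figure 14.5.5.2.17, and make the label, unit and reference limits match what was recorded.
5. Add the chloride scatterplot to the output list; SAP 12.4 already requires it.

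The cost is a few lines of SAP text and up to six more parameters run through table and figure programs already planned for the other 19. If none was captured, step 3 is a short statement in SAP 2.1. If the SAP is already final, the change belongs in the complementary SAP that protocol 7.1.9 provides for. No new data collection is involved; the report may have to say that some planned tests were not recorded.
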